## 9 Withdrawal Criteria

Subjects who have signed an informed consent form may be withdrawn from this study if they become unwilling or unable to comply with follow-up requirements, if they withdraw their consent, or if the investigator determines the subject should no longer continue in the study. Regardless of the

reason for withdrawal, data available for the subject at the time of withdrawal, including the reason for withdrawal, will be collected and entered in EDC. All practical efforts will be made to obtain the final AR status, retreatment status, and IPSS information.

## 10 Subject Procedures: Prospective Cohort

---

### 10.1 Subject Identification and Recruitment

---

Potential candidates for study will be identified through several paths (See **Figure 4**) with close oversite of the PI. The enrolment rate targeted is (2) subjects per month at each site which will be accomplished only if PI plays an active role in recruitment. PI contribution will vary per site, but could include training additional staff (such as research fellows), reviewing medical records with or in parallel to Research Coordinating Nurses (RC), and implementing awareness programs for local consultants and GPs. A plan should be established for a focused and efficient review of NHS medical records, along with monitoring BPH surgery waiting lists. Weekly time should be budgeted to execute the review plan and to discuss progress within the research team. Direct advertising is not planned, but may be implemented if enrolment proves challenging. The study will be posted on clinicaltrials.gov in advance of first subject, and other similar websites may be added. Sponsor may host web based meetings for the Research Coordinators to share expertise and troubleshoot any recruitment obstacles. Study accoutrements for recruitment will be provided by Sponsor such as posters, post-cards, and template letters to physicians, and language to post on research websites, provided they are first approved by the EC if intended for patients.

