Men failing a single TWOC have limited options to restore voiding. Long-term catheter management may be elected, either indwelling or intermittent clean catheterisation (CISC), which carries a burden of maintenance and frequent UTIs (over half will experience). Catheter use carries with it risk of haematuria, and less common AEs such as urethral diverticula and ischemic necrosis of the penis. Many patients will opt instead to undergo an invasive BPH surgery such as TURP, PVP or HoLEP. These surgical options are known to be effective in treating BPH, however, the safety and recovery profile are more severe than a minimally invasive procedure including possible permanent sequelae. The complication rates vary depending on procedure, but common to all include infection, bleeding, pain, stress incontinence, sexual dysfunction, incontinence, delayed recovery up to 3-6 months and re-treatment. The other reality of invasive surgery in U.K. is the long waiting period to secure OR time that extends time on catheter significantly. The waiting period averages 30 weeks to procedure after counselling the patient.

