The early UroLift studies described in section 5 above excluded subjects in urinary retention in order to provide non-confounding data on subjects with possible advanced bladder disease. The clinical studies also required BPH medication washout which is known to be effective in short term treatment of AR. This population is not contraindicated; however, no study yet exists to assess if its efficacy and safety are similar to the voiding subjects. The UroLift System is designed to immediately de-obstruct the prostatic lobes without tissue damage, thereby reducing the pressure required to initiate micturition. Because of this mechanism, it is hypothesised that urinary retention may resolve after PUL removes the mechanical cause of the AR. The PUL technology could offer patients a shorter wait time, and a safety profile that could be an attractive option for AR patients. As discussed above, the PUL procedure is a minimally invasive technique for BPH patients with demonstrated effectiveness and majority of adverse events mild or moderate and transient. Recovery to normal activity was reported at 8-9 days in the L.I.F.T. study. Additional benefits include short operative times, minimal bleeding, shorter hospital stay and maintenance of normal sexual function. Treatment under local anaesthesia is an emerging technique offering rapid treatment and recovery in the clinical setting.

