### 8.1 Inclusion Criteria

---

Subjects enroled in this clinical study must meet all of the following criteria.

1. Male gender
2. Diagnosis of symptomatic BPH
3. Age  $\geq$  50 years
4. Prostate volume  $\leq$  100 cc per ultrasound (US)
5. Acute urinary retention with at least one failed trial without catheter (TWOC) while on alpha blocker

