### 13.1 Anticipated clinical benefits

There are no guaranteed benefits from participation in this study. Extensive clinical experience with the UroLift System, in absence of urinary retention, has established the safety of the procedure and effectiveness of the UroLift System. For those subjects who suffer from acute urinary retention and BPH, the UroLift System has the potential to address their condition without heating, burning, or cutting tissue. The UroLift System has received CE Mark in Europe, allowing it to be marketed to the United Kingdom. In published clinical studies, it has been shown to significantly reduce LUTS rapidly while preserving important functions, such as sexual function and continence.

Because the PUL procedure takes a prostatic tissue sparing approach rather than tissue resection or ablation, there are potential benefits over conventional surgical treatments for BPH. There is a potential that the PUL procedure requires less anaesthesia and causes less bleeding and sexual dysfunction than more invasive modalities such as transurethral resection of the prostate (TURP) or laser resection. There is a potential that there may be a decrease in procedure time, catheter time, and/or post-operative recovery time when compared to other surgical therapies. There is potential that the time waiting for a procedure while catheterised is reduced. Information gained from this study may be used to benefit future subjects and help guide their therapy.

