### **Retrospective Arm**

The following baseline and procedural data points will be summarised for both the retrospective and the prospective arms. Although the study is not powered to make comparisons between the retrospective surgical patients and the prospective Urolift subjects, comparisons in the observed data will be made statistically. Continuous variables will be compared using a t-test or non-parametric alternative, binary data points will be compared using chi-square or Fisher's exact test.

- 1) Baseline demographics

- 2) Duration of catheterisation to procedure (days)
- 3) Procedure time
- 4) Hospitalisation time

The following outcomes post procedure will be summarised for the retrospective surgical group and will compared to the results obtained in the prospective study. The statistical significance of any observed differences will be assessed.

- 1) Total numbers of related AE, SAE, and Clavien-Dindo  $\geq$ IIb individually
- 2) Percent procedure/device related AE rates by month post index procedure and by severity
- 3) Retreatment post index intervention by time to event and by month
- 4) Medical treatment post index intervention by time to event and by month
- 5) Urinary retention recurrence rates at 1 month, 6 weeks and at 3, 6 and 12 months
- 6) Post-procedure TWOC success percent
- 7) Catheterisation use

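### Catheter time before PUL is tested against completed surgical waits, but PUL men may come off the surgery waiting lists, so the test cannot separate PUL from recruitment

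*Combined protocol and SAP*

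**What the plan says.** **How PUL men are found.** Section 10.1 says "Potential candidates for study will be identified through several paths" and tells sites: "A plan should be established for a focused and efficient review of NHS medical records, along with monitoring BPH surgery waiting lists". It adds: "The enrolment rate targeted is (2) subjects per month at each site which will be accomplished only if PI plays an active role in recruitment". It does not say what share of men should or may come from the lists.

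**Who is eligible.** The retention criterion in Section 8.1 is "Acute urinary retention with at least one failed trial without catheter (TWOC) while on alpha blocker". Neither 8.1 nor 8.2 limits how long a man has been catheterised or listed for surgery.

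**Who the comparators are.** Section 15.3.1 selects men who had invasive BPH surgery while in retention, at the site, between June and December 2015. Their waits are complete by construction.

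**What is compared.** In Section 16.6, Retrospective Arm, item 2 of the baseline and procedural list is "Duration of catheterisation to procedure (days"). Continuous items in that list are to be compared by a t-test or a non-parametric alternative. No adjustment is described. The Protocol Summary also names catheter duration before treatment, PUL against surgery, as additional assessment 5.

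**What benefit is suggested.** Section 6 gives the surgical wait: "The waiting period averages 30 weeks to procedure after counselling the patient". It then says "The PUL technology could offer patients a shorter wait time". Section 13.1 says "There is potential that the time waiting for a procedure while catheterised is reduced". Section 13.9 expects the benefit of offering UroLift to show through the comparison with the surgical dataset.

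**The concern.** The two arms measure different things under one label. For a surgery man, the interval is a finished wait for an operation. For a man taken off a waiting list, it is the part of his surgical wait that had passed when the study found him, plus the time the study took to consent and treat him. For a man approached soon after a failed TWOC, it is mostly the study's own lead time. If PUL can really be scheduled sooner than surgery, that effect is in the PUL interval too, but it cannot be isolated.

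The plan does not start the clock at a common point, does not make recruitment path an analysis factor, and gives no caution on this item. The bias checklist in Table 12 covers how surgical charts are selected and abstracted, not how PUL men are found. Capturing catheter history identically in both arms would not cure this.

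At stake is how one p-value is read. A shorter catheterised wait is a suggested benefit of PUL, so a significant result on this item would naturally be taken as support for it.

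**Working it through.** The plan states no effect size or power for this item, so there is no figure to reproduce. The check asks what the planned test would show for **men drawn from the lists** if PUL had no effect on the wait.

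**Inputs**
- Mean surgical wait: 30 weeks (Section 6). This runs from counselling, so it only approximates catheter time. If the catheterised time before counselling is alike in both arms, it cancels from the difference in means.
- Variability of waits: not given. Assumed gamma, with coefficient of variation (CV) 0.25 to 1.25.
- Time from being found to PUL: not given. Assumed 4 weeks, and never later than the man's surgery would have been.
- PUL men: 55, the maximum in Section 7. Surgery men: not fixed in the plan; 30, 55 and 100 were tried.
- Test level: not given. Assumed two-sided 0.05, Welch t-test.

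**Two ways to find a man on a list**, at a uniform point of his wait W:
- (a) Every listed man is equally likely to be found. Mean elapsed wait = 30/2 = 15 weeks.
- (b) The list is sampled at one moment, so long waiters are over-represented. Mean elapsed wait = E[W²]/(2E[W]) = 30(1 + CV²)/2. For CV 0.5 this is 30 × 1.25/2 = 18.8 weeks.

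**Hand check with the lead time included**
- Fixed 30-week wait: 15 + (4 × 26 + 8)/30 = 18.7 weeks. Difference from surgery: 18.7 - 30 = -11.3 weeks.
- Exponential waits under (b): 30 + 30(1 - e^(-4/30)) = 33.7 weeks. Difference: +3.7 weeks.

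**Simulation**, 55 against 55 men, 1,500 trials per row (difference is PUL minus surgery, in weeks):

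| CV | (a) difference | (a) trials with p < 0.05 | (b) elapsed before lead time | (b) difference | (b) trials with p < 0.05 |
|---|---|---|---|---|---|
| 0.25 | -11.3 | 100% | 15.9 | -10.4 | 100% |
| 0.50 | -11.4 | 99.0% | 18.8 | -7.6 | 75.9% |
| 0.75 | -11.5 | 87.8% | 23.4 | -2.9 | 10.5% |
| 1.00 | -11.7 | 68.8% | 30.0 | +3.5 | 9.7% |
| 1.25 | -12.1 | 53.3% | 38.4 | +12.0 | 37.7% |

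With no PUL effect, 5% would be expected in the two rejection columns. With 30 or 100 surgery men the mean differences are practically the same. The rejection rates shift: at CV 0.75 under (b), for example, they are 6.1% and 13.3%.

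Recruitment from lists can thus produce a significant difference in either direction. Which one depends on the spread of waits and on how the list is searched, and the plan fixes neither.

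**The case against.** The best defence is that little hangs on this item. Section 16.6 says the comparison is not powered, Section 16.7 sets no success criterion, and Section 13.9 calls the design qualitative. Item 2 sits with baseline and procedural data, apart from the post-procedure outcomes, and Section 6.4 also treats pre-procedure catheter time as a possible influence on durability. The benefit wording is hedged, and Section 13.1 says no benefit is guaranteed. Some limits on comparability come with any retrospective cohort. Waiting lists are only one path, and their share could be near zero. Table 6 does collect catheter history and duration, and the eCRFs are not part of the documents, so recruitment path or listing date may be captured there.

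Most of this stands and limits the severity. It does not remove the point. Low power is about missing real differences, whereas here a difference can arise with no PUL effect. The plan still calls for the test, and the benefit statements remain.

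Two stronger readings are tempting and should be resisted.
- A reader might infer that recruitment, **not PUL**, sets the interval. The documents do not show this. The list share is unknown, procedure slots are nowhere described, and the free supply of study devices (Section 18) is not linked to timing. A real scheduling advantage may be part of the interval.
- A reader might infer that recruitment alone could create a gain of 0 to 26 weeks. The 26 is 30 - 4: a PUL arm with no list men, all treated 4 weeks after catheterisation. That could be the genuine shorter wait the protocol hopes for. The 0 comes from giving list men under exponential waits no lead time. With the same 4 weeks added, PUL looks about 4 weeks worse.

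**Conclusion.** The concern holds in a limited form. Section 10.1 allows PUL men to be found on surgical waiting lists, and Section 16.6 tests their pre-procedure catheter time against completed surgical waits. That test cannot separate PUL from the way men were found and scheduled, so a significant difference cannot support the shorter wait suggested in Sections 6 and 13.1, and a null result cannot refute it.

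For list men only, the illustrated spurious difference runs from about -12 to +12 weeks. This rests on the 30-week mean as a stand-in for catheter time, gamma waits with CV 0.25 to 1.25, a 4-week lead time and no PUL effect. In a mixed sample the size also depends on the unstated share of list men and on how soon the others are treated. Neither size nor direction is fixed.

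Severity is minor to moderate: this is an unpowered feasibility comparison, and no primary, safety or stopping decision depends on it.

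**What to change.** **Table 6.** Add three fields:
- recruitment path (surgical waiting list, new failed TWOC, other);
- start date of catheterisation for the current retention episode, since the present catheter row asks for history and duration with the time frame limited to the most recent;
- date listed for surgery, if listed.

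If the eCRF already holds any of these, a reference to it is enough.

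**Section 16.6, Retrospective Arm.** Take item 2 out of the significance tests. Report it descriptively in both arms, split by recruitment path in the PUL arm. Show consent-to-PUL time separately. State that pre-procedure time in the PUL arm partly reflects trial recruitment and scheduling.

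**Cost.** Sites record a few more fields, and the wait comparison loses its p-value. No patient procedure changes. The same fields would help with the Section 6.4 question on pre-procedure catheter time and durability, and with planning the larger trial.

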### 10.2 Screening Procedures

---

#### 10.2.1 Informed Consent Process

The investigator or trained designee will discuss the study background along with the benefits and risks of the PUL procedure, participation, and other study procedures. Ample time and opportunity for candidate to inquire about details of the trial and to decide whether or not to participate in the trial should be given. All questions about the trial should be answered to the satisfaction of the subject, or the subject's legally acceptable representative.

For this study, the potential subject must sign the consent form that has been approved by the study site's Ethics Committee (EC). Failure to provide informed consent renders the subject ineligible for the study.

Subjects who appear to generally meet the study Inclusion/Exclusion criteria will be asked to sign the EC approved Informed Consent form before any study-specific tests or procedures are performed.

A copy of the signed and dated written consent form shall be given to the subject, an original shall be filed in the subject's medical record, and a copy maintained with the site's research documentation. Subjects should first sign the informed consent prior to undergoing any non-standard of care testing required by this study protocol.

Throughout the study, should there be important updates to the protocol and/or additional risks identified, a new EC approved consent form will require the subject's signature and date.

#### 10.2.2 Determining Eligibility

To minimise stress and discomfort to the subject, some of the procedures that were documented and performed prior to subject informed consent, but within the timeframes specified below (

**Table 5**) may be used as a guideline for eligibility and baseline data. To further minimise burden on the subject, some eligibility tests are allowed on day of index procedure, therefore, proper expectations and alternatives will be discussed and planned with the subject. **Table 5** below provides a guideline of each of the inclusion and exclusion criteria timeframe and instructions. Subjects enroled without meeting all criteria will be considered a significant violation, and data may be excluded from analysis.

**Table 5: Eligibility Procedures**

Screening activity	Relevant Eligibility Criteria	Time Frame	Instructions
Ultrasound	
 
• Prostate volume ≤ 100 cc per ultrasound rule out enlarged middle (median) lobe
 
	During screening or just prior to procedure unless on file within 6 months of Index Procedure.	
 
• Can be utilised if performed within 6 months of UroLift procedure/ enrolment, provided there is source documentation.
 
• See section 10.13.2 for instructions.
 

Cystoscopy	
 
• Urethral conditions that prevent insertion
 
• Rule out obstructive or protruding median lobe
 
	In screening or adjacent to (prior) on day of index procedure.	
 
• Complete eCRF for cystoscopy performed.
 
• Save digital recording and submit to NeoTract.
 

Medical History by PI assessment	
 
• Life expectancy estimated to be less than 5 years
 
• Co-morbidities that could impact the study
 
• Diagnosis of symptomatic BPH
 
• Acute or chronic renal failure
 
• Chronic retention volume of >1500 mL
 
	In screening up to index procedure; PI assessment should be as close to index procedure as possible.	
 
• Patients with terminal conditions will be excluded.
 
• Significant co-morbidities that impact life expectancy or ability to return for follow-up, or exposes patient to unreasonable risk should be excluded.
 
• AR precipitated for reasons other than BPH must be confirmed and excluded.
 
• Signs of renal failure should be ruled out per SOC.
 

Screening activity	Relevant Eligibility Criteria	Time Frame	Instructions
Medical History by medical database	
 
• Prostatitis requiring treatment (antibiotics) within the last year
 
• Known bladder stone within the prior 3 months or treatment within 12 months
 
• Previous BPH or pelvic surgical procedure
 
• Prostate or bladder cancer history
 
• Prostate biopsy (allowed if negative and <math>\geq 6</math> wks)
 
• Neurogenic or atonic bladder
 
• If available, pre-procedure IPSS, peak flow rate, and PVR within 6 months
 
	In screening up to index procedure; review of database should be completed as close to index procedure as possible.	
 
• These criteria should be confirmed through patient interview and consistent with medical chart. Diagnostic testing not required unless symptomatic.
 
• A thorough medical history should be documented to assist with adverse event reporting after enrolment, as each AE will require assessing if pre-existing or new.
 

Medical History by patient interview	
 
• Unable or unwilling to complete all required questionnaires and follow up assessments
 
• Desire to maintain fertility post procedure
 
• Currently enroled in any other clinical research study that has not completed primary endpoint
 
	Prior to procedure	
 
• Erectile health will be a part of the questionnaires and participants should be willing to complete.
 

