**Table 2 Definitions**

Adverse event (AE)	An adverse event (AE) is defined as any undesirable medical occurrence in a clinical trial subject, whether it is considered to be related to the device or not, that includes a clinical sign, symptom, or condition.  Once a subject is enroled, all AEs must be reported through follow-up period. Only exacerbated conditions or new onset qualify as an AE. Principal Investigator will assess severity, relatedness, serious or unexpected.
Alternative Surgical Intervention	A post-index procedure surgery, other than PUL, to treat BPH.
Acute Urinary Retention	Painful inability to void and a residual volume < 1500 mL.
Invasive BPH surgery	
 
• Transurethral resection of the prostate (TURP)
 
• Transurethral Laser (PVP, HoLEP or Interstitial)
 
• Open Prostatectomy
 

Index procedure	The first procedure to which subjects are enroled.
Precipitated AR	Acute urinary retention that develops in response to a trigger such as UTI, anaesthesia, surgery, medications with sympathomimetic or anticholinergic effects.
Serious Adverse Event (SAE)	
Serious Adverse Event (SAE) is defined as untoward occurrence that: (a) results in death; (b) is life-threatening; (c) requires hospitalisation or prolongation of existing hospitalisation (d) results in persistent or significant disability or incapacity; (e) consists of a congenital anomaly or birth defect; or (f) is otherwise considered medically significant by the investigator.
 
(in-patient hospitalisation is at least 24 consecutive hours)

Unexpected Adverse Event	An unexpected adverse event is an event which by nature, incidence, severity or outcome has not been identified in the current version of the Sponsor risk management files.
Spontaneous AR	Associated with older age, BPH, elevated PSA, or presence of severe LUTS.
PUL Procedure Time	Time from first device insertion to last device removed.

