### 8.2 Exclusion Criteria

---

Subjects will be excluded from the study if any of the following conditions apply.

1. An obstructive or protruding median lobe of the prostate
2. Previous BPH surgical procedure
3. Previous pelvic surgery (i.e. incontinence sling, trauma repair, penile implants, artificial sphincter) or irradiation
4. Urethral conditions that prevents insertion and delivery of device system into bladder (i.e. urethral strictures, meatal stenosis, bladder neck contracture)

5. Chronic retention volume of >1500 mL
6. Has not had prostate cancer excluded
7. History of prostate or bladder cancer
8. Biopsy of the prostate within the 6 weeks prior to Index Procedure
9. History of neurogenic or atonic bladder
10. Acute or chronic renal failure
11. Known coagulopathies or subject on anticoagulants within 3 days of index procedure (excluding up to 100mg ASA)
12. Known bladder stones within the prior 3 months or treatment within 12 months
13. Prostatitis requiring treatment (antibiotics) within the last year
14. Other co-morbidities that could impact the study results such as:
  - severe cardiac arrhythmias uncontrolled by medications or pacemaker
  - congestive heart failure NYHA III or IV
  - history of uncontrolled diabetes mellitus
  - significant respiratory disease in which hospitalisation may be required
  - known immunosuppression (i.e. AIDS, post-transplant, undergoing chemotherapy)
15. Life expectancy estimated to be less than 5 years
16. Desire to maintain fertility post procedure
17. Unable or unwilling to complete all required questionnaires and follow up assessments (e.g. lives out of area)
18. Unable or unwilling to sign informed consent form
19. Currently enroled in any other clinical research trial that has not completed the primary endpoint

Refer to Section 15.3 for the modified enrolment criteria for the retrospective arm.

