## 15.3 Modified Enrolment Criteria for Retrospective Arm

### 15.3.1 Retrospective Inclusion Criteria

Patients enroled in this study must meet the following criteria:

1. Male gender
2. Diagnosis of symptomatic BPH
3. Age  $\geq$  50 years
4. Presented with acute urinary retention with at least one failed trial without catheter prior to invasive surgery (index procedure)
5. Underwent invasive BPH surgery (TURP, HoLEP, etc.) while in retention and performed by site between June 01, 2015 and December 31, 2015.
6. Prostate volume  $\leq$  100 cc as measured by ultrasound, specimen (tissue) weight, or other standard method for prostate evaluation

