**Table 12 Retrospective Chart Review Design Quality Checklist**

Issue and Suggested Solution		Study Design
Chart Review Inappropriate for Study Question		

 
Establish whether necessary information is available in the chart.
 
Define outcome variables to be collected a priori.
 
Establish if there are sufficient charts to perform the analysis with adequate precision.
 
		
 
Participating sites are research centres, two sites have presented their own UroLift datasets at medical conferences.
 
The EDC system (host of the eCRFs) and source worksheets will guide the abstractor on exact data collection requirements.
 
Participating PIs were qualified due to their high number of BPH patients they treat.
 

Investigator Conflict of Interest or Bias		

 
Declare any conflict of interest.
 
Provide evidence of Ethics Committee approval.
 
Submit the data collection form, as well as the coding rules and definitions.
 
		
 
Financial Disclosure and conflict of interest forms will be completed by all Principal Investigators.
 
A regulatory binder will be maintained for HRA and EC correspondence including approval materials.
 
Study will utilise EDC with eCRF completion instructions. MedDRA coding will be used and embedded in the EDC.
 

Patient Sample is Non-Representative		

 
Case selection or exclusion using explicit protocols and well described the criteria.
 
Ensure all available charts have an equal chance of selection.
 
		
 
Study design requires that all surgeries during a set amount of time are evaluated for inclusion, and criteria are well matched to the prospective investigation.
 
The NHS trust system is consistent across centres.
 

Chart Abstraction is Not Systematic (Misclassification Bias)		

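### Table 5 bars retention precipitated by non-BPH causes from the PUL arm, but Section 8.2 does not list the rule and the surgical comparator has no equivalent

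*Combined protocol and SAP*

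**What the plan says.** All references are to the combined protocol and SAP.

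- **Table 5 (PUL arm, medical history by PI assessment):** "AR precipitated for reasons other than BPH must be confirmed and excluded". The same row names the five eligibility criteria it serves: life expectancy, co-morbidities, symptomatic BPH, renal failure and a chronic retention volume limit. Cause of retention is not among them.
- **Section 8.1 (PUL inclusion):** "Acute urinary retention with at least one failed trial without catheter (TWOC) while on alpha blocker". No cause is specified.
- **Section 8.2 (PUL exclusion):** 19 items. The only one that names retention is "Chronic retention volume of >1500 mL".
- **Section 15.3.1 (retrospective inclusion):** "Presented with acute urinary retention with at least one failed trial without catheter prior to invasive surgery (index procedure", together with surgery performed while still in retention. No cause is specified, and none of the eight exclusions in Section 15.3.2 supplies one.
- **Table 2:** defines precipitated AR as "Acute urinary retention that develops in response to a trigger such as UTI, anaesthesia, surgery, medications with sympathomimetic or anticholinergic effects" and also defines spontaneous AR. Neither criteria list uses either term.
- **Section 10.2.2:** says that Table 5 "below provides a guideline of each of the inclusion and exclusion criteria timeframe and instructions", and that "Subjects enroled without meeting all criteria will be considered a significant violation, and data may be excluded from analysis".
- **Table 12:** gives as a safeguard against a non-representative sample that "criteria are well matched to the prospective investigation".

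**The concern.** An exclusion that uses the word must, but appears only in a screening table, has no numbered criterion behind it. That matters in two ways.

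First, the comparison. Abstractors building the surgical group work from Section 15.3, not from Table 5, so one arm is filtered by cause of retention and the other is not. Section 16.6 then tests differences in TWOC success, retention recurrence and retreatment, the outcomes most plausibly affected by why a man went into retention. Cause is not a named abstraction item, so the imbalance could not be reliably described or adjusted for later.

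Second, the per-protocol set. Section 16.2 removes significant violations that affect data integrity, and Section 16.5 reports the primary assessment in that set as well as in ITT. A man with BPH plus a trigger can satisfy every item of Section 8 and still arguably breach Table 5. The plan does not say how he is classified.

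The study is a feasibility study, but the protocol summary and Section 7 make assessment of the inclusion criteria one of its aims, and Section 16.7 says its results will inform a future controlled study.

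**Working it through.** The plan gives no figure on this point, so the check is a comparison of texts.

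**Step 1. The two arms side by side**

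| Feature | PUL arm | Retrospective arm |
|---|---|---|
| Symptomatic BPH required | Yes (8.1) | Yes (15.3.1) |
| Failed TWOC required | Yes, on alpha blocker (8.1) | Yes, no alpha blocker condition (15.3.1) |
| Neurogenic or atonic bladder, prostate or bladder cancer, recent stones, treated prostatitis | Excluded (8.2) | Excluded (15.3.2) |
| Urethral stricture preventing device insertion | Excluded (8.2) | Not listed |
| Retention precipitated by a non-BPH cause | Excluded by Table 5 only | Not listed |
| Cause of retention as a named data item | No; catheter indication is recorded (Table 6) | No (15.8.1) |

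**Step 2. What gap remains.** Both lists already remove several specific non-BPH causes. What is left is mainly the Table 2 triggers (infection, anaesthesia, surgery, drugs) in men who also have BPH, plus stricture in the surgical arm.

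**Step 3. Is the Table 5 rule clear for such a man?** No. Table 5 speaks of precipitation by something other than BPH. Table 2 defines precipitated AR by the presence of a trigger and says nothing about coexisting BPH. Section 6 lists infection among the triggers but treats drugs and anaesthetics as contributory factors, whereas Table 2 calls them all triggers. A man with BPH and a drug trigger can be read either way.

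**Step 4. What the size depends on.** Let q be the share of precipitated cases present in the surgical arm only, and d the TWOC success rate in precipitated cases minus that in spontaneous cases. The surgical arm's rate is then (1 − q) × p + q × (p + d) = p + q × d, where p is the rate in spontaneous cases. The shift is q × d.

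The documents give neither q nor d. As pure illustration, with both assumed:

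- q = 10%, d = 10 points: 0.10 × 10 = 1 point.
- q = 20%, d = 20 points: 0.20 × 20 = 4 points.
- q = 40%, d = 30 points: 0.40 × 30 = 12 points.

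For scale, the 95% half-width for a single proportion at the maximum PUL sample of 55 is 1.96 × √(0.6 × 0.4 / 55) = 12.9 points at 60% success and 1.96 × √(0.9 × 0.1 / 55) = 7.9 points at 90%. The plan states no size for the surgical arm, so no half-width for the difference can be given.

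**The case against.** The strongest reply is that Table 5 is not a rival rulebook. Section 10.2.2 presents it as the instructions for applying the Section 8 criteria, it covers every PUL site, and its rule fits the population in the protocol summary, which is retention secondary to BPH. Section 8 is silent; it does not expressly admit such men. This stands against one tempting inference, that some sites will enrol triggered retention and others will not. That is possible, because the table is called a guideline and its wording is ambiguous, but the documents do not show it.

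A second reply is that other criteria shrink the gap. Both arms require symptomatic BPH and a failed TWOC, and the surgical men were still in retention at operation, after a UK wait that Section 6 puts at 30 weeks on average. Men whose trigger cleared would often have recovered voiding before surgery. This also stands. It suggests a smaller q, and perhaps a smaller d, without making either zero.

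A reader might also infer that the mismatch flatters the device. The documents do not support that. If Table 5 is followed and triggered cases do void more readily, the extra cases sit in the surgical arm and raise its TWOC rate. No passage establishes that they void more readily after a procedure.

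Finally, Section 16.6 concedes that the comparison is unpowered, Section 16.7 sets no success criterion, and the retrospective criteria are openly labelled as modified. These lower the stakes. They do not answer the problem, because the comparisons will still be tested for significance and Table 12 relies on the match in criteria as a safeguard against bias.

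**Conclusion.** The point holds as an internal inconsistency that builds a selection difference into the comparison. The PUL arm is restricted by cause of retention through Table 5, Section 8.2 has no matching criterion, and the surgical arm has no such restriction and no named item from which cause could be recovered. Per-protocol status of a PUL subject with BPH plus a trigger is undefined.

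The size is unknown and the direction is not established. The 1 to 12 point range is illustrative only and rests entirely on assumed values of q and d. Neither divergence between sites nor bias in favour of PUL should be read into the finding. Correction is worthwhile because it is cheap and because, without it, the imbalance cannot be examined after the fact. No numerical error in the plan is involved, and this point takes no view on which eligibility rule is clinically right.

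**What to change.** 1. Reconcile Table 5 with Section 8.2 and the Table 2 definitions, and say explicitly how a man with both BPH and a trigger is classified.
2. State whichever rule is kept in the same words in Sections 8.2 and 15.3.2.
3. State in Section 16.2 whether a PUL subject who departs from that rule is a significant violation and leaves the per-protocol set.
4. Record type of retention (spontaneous, precipitated, unknown) in both arms: add it to the PUL baseline data and to Section 15.8.1, and summarise it with the baseline characteristics in Section 16.6.
5. Add to Section 16.6 a between-arm sensitivity analysis restricted to spontaneous retention for TWOC success, retention recurrence and retreatment. If the exclusion is kept in both arms, this mainly tests the handling of men whose type is unknown. If it is dropped, it carries more weight.

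**Cost:** two lines of criteria, one eCRF field, a sentence on the per-protocol set and one extra analysis. A few retrospective men may be excluded or classed as unknown because the chart does not give the cause. If exclusion proves impractical in the retrospective arm, recording type of retention alone would still make the imbalance visible.
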